## **8. PHARMACOKINETIC ANALYSES**

### **8.1. PK Sample Collection**

Intensive PK samples are collected on Day 8 of Cycle 1 at 0 (pre-dose), 1, 2, 3, 4, 6, 8, and 12 hours post-dose of ENTO.

Sparse PK samples are collected at pre-dose and 2 hours post-dose of ENTO on (1) Days 1, 14, and 28 of Cycle 1; (2) Day 28 of Cycle 2 and subsequent cycles.

Concentrations of ENTO in plasma will be determined using a validated bioanalytical assay.

### **8.2. Statistical Analysis Methods**

#### **8.2.1. Plasma Concentration**

Plasma PK sampling details by subject including nominal collection time, actual dosing time and actual collection time, calculated time postdose of sample collection, differences in scheduled and actual draw times, sample age, and sample ENTO concentration will be provided in the listing.

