**Criteria for Evaluation:**

**Safety:** Grading of adverse events and laboratory abnormalities. The CTEP Active Version of the NCI Common Terminology Criteria for Adverse Events (CTCAE) version 4.03 will be utilized for Adverse Event (AE) reporting.

**Efficacy:** Assessment of clinical response in subjects with hematologic malignancies other than AML will be according to the latest set of published response criteria. Assessment of clinical response in subjects with AML will be according to the modified International Working Group criteria and will include findings on examination of blood, bone marrow and physical examination.

**Pharmacokinetics:** Plasma drug concentrations will be analyzed for determination of ENTO PK parameters.

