**Statistical Methods:**

Appropriate data analysis sets will be defined. The full-analysis set (FAS) will include all subjects who receive at least 1 dose of study drug (ENTO). The DLT analysis set includes subjects in FAS with sufficient drug exposure or who experience a DLT during the DLT assessment window. Other data sets will be defined and will include subjects who have the necessary baseline and on study measurements to provide interpretable results for specific parameters of interest.

Subject characteristics and study results will be described and summarized for the relevant analysis sets. Descriptive summaries will be prepared to show the number of subjects, mean, standard deviation (StD), 95% confidence intervals (CIs) the mean, median, minimum, and maximum for continuous variables; counts, percentages, and 95% CIs on the percentage for categorical variables. Time-to-event endpoints (eg, RFS, EFS, and OS) will be analyzed using Kaplan-Meier (KM) methods. The KM estimate of the survival function will be computed and the results will be presented using KM curves. The median with the corresponding 95% CI, the 25%, and 75% percentiles for these endpoints will be provided.

Data regarding study treatment administration, study drug compliance, safety variables, and post study therapies will be described and summarized using FAS. Using data from the relevant evaluable data sets, study drug plasma concentrations will also be described and summarized.

---

This study will be conducted in accordance with the guidelines of Good Clinical Practice (GCP) including archiving of essential documents.

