### **8.1.3. Secondary Endpoints**

The secondary endpoints of this study are:

Safety

- Occurrence of AEs, laboratory findings and findings on physical exam not defined as DLTs

Pharmacokinetics

- Determination of the PK parameters of ENTO based on plasma concentrations

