#### **8.2.1.3. Pharmacokinetic Analysis Sets**

Pharmacokinetic Analysis Sets include all subjects in FAS who have necessary baseline and post-treatment assessments in order to provide interpretable results for the specific parameters of interest.

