### **8.7. Pharmacokinetic Analysis**

Concentrations of ENTO and its metabolites (if applicable) in plasma will be determined using a validated bioanalytical assay. Calculated pharmacokinetic parameters will include  $AUC_{\tau}$ ,  $C_{\max}$ ,  $T_{\max}$ ,  $t_{1/2}$ , and  $C_{\tau}$  (if applicable). Pharmacokinetic parameters will be listed and summarized for ENTO and its metabolites (if applicable) using descriptive statistics (eg, sample size, arithmetic mean, geometric mean, % coefficient of variation, standard deviation, median, minimum, and maximum). Plasma concentrations of ENTO and its metabolites (if applicable) over time will be plotted in semi logarithmic and linear formats as mean  $\pm$  standard deviation.

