## 1. INTRODUCTION

This statistical analysis plan (SAP) describes the statistical analysis methods and data presentations to be used in tables, figures, and listings (TFLs) in a synoptic study report (CSR) for Study GS-US-429-4104. This SAP is based on Protocol GS-US-429-4104 Amendment 3 dated 23 August 2017 and the electronic case report form (eCRF). The SAP will be finalized before database finalization. Any changes made after the finalization of the SAP will be documented in the CSR.

The study was originally designed to evaluate the safety, tolerability, and pharmacokinetics of entospletinib (ENTO) in 2 stages: (1) ENTO monotherapy (Group A) for relapsed or refractory hematologic malignancies; (2) ENTO in combination with cytarabine and daunorubicin (Group B) for AML. However, per the Sponsor's decision, only the monotherapy stage is conducted with full enrollment of Group A, and the study will be terminated early without opening enrollment in Group B. The decision to terminate the study was not due to any safety concerns. Therefore, a synoptic CSR will be generated, and this SAP describes the analyses for the monotherapy part (Group A) only.

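### SAP section 8 plans only a concentration listing, so the protocol's PK parameters, summaries and plots for the secondary PK endpoint drop out without being declared

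*SAP*

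**What the plan says.** **Protocol.** The secondary PK endpoint in 8.1.3 is "Determination of the PK parameters of ENTO based on plasma concentrations". The synopsis, under Criteria for Evaluation, gives the same purpose: "Plasma drug concentrations will be analyzed for determination of ENTO PK parameters". Section 8.7 names AUCtau, Cmax, Tmax, t1/2 and, if applicable, Ctau. It then states: "Pharmacokinetic parameters will be listed and summarized for ENTO and its metabolites (if applicable) using descriptive statistics". Concentrations "over time will be plotted in semi logarithmic and linear formats". Under Statistical Methods the synopsis adds that "study drug plasma concentrations will also be described and summarized". Section 8.2.1.3 defines the PK Analysis Sets by the data needed "in order to provide interpretable results for the specific parameters of interest".

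**SAP.** Section 1 explains that the study stops early without opening Group B, that a synoptic CSR will be written, and that "this SAP describes the analyses for the monotherapy part (Group A) only". The Group A PK objective stays in 1.1.2. The PK Analysis Sets stay in 3.1.3 and are assigned to the 400 mg BID column in 3.2. Section 8.1 describes intensive sampling on Cycle 1 Day 8 at pre-dose and 1, 2, 3, 4, 6, 8 and 12 hours. Section 8.2 has one subsection, 8.2.1, with one output, a by-subject listing of dosing and sampling times and results: "sample age, and sample ENTO concentration will be provided in the listing".

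**The concern.** The endpoint is a set of parameters, and the SAP plans none of them. A listing of concentrations is raw data. It gives no estimate of exposure, so the Group A PK objective would be reported without an answer even though the 0-12 h profile that supports one is scheduled.

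Nothing tells the reader that the protocol analysis was cut back. If parameters are derived after the data are seen, two choices will not have been fixed beforehand: whether actual or nominal times are used, and whether the pre-dose or the 12-hour sample defines Ctau.

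The SAP also disagrees with itself. Section 3.7 writes rules for concentration summary statistics by time point, while section 8 plans no such summary.

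**Working it through.** No sample size, power or error rate bears on this point, so the check is an item-by-item comparison of planned outputs.

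**1. PK outputs in the protocol against SAP section 8**

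| Output | Protocol source | In SAP 8.2? |
|---|---|---|
| Parameter listing | 8.7 | No |
| Parameter summary statistics | 8.7 | No |
| Linear concentration-time plot | 8.7 | No |
| Semi-log concentration-time plot | 8.7 | No |
| Concentration summary | Synopsis, Statistical Methods | No |

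Count: 1 + 1 + 2 + 1 = 5 outputs in the protocol, 0 in the SAP. The SAP plans 1 concentration listing. The result does not depend on how outputs are counted:
- Treating the two plot formats as one output gives 0 of 4.
- Crediting the concentration listing as a protocol output, under the general by-subject listing rule in protocol 8.3, gives 1 of 6.

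In every version the parameters, summaries and plots are absent.

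**2. Parameters.** Protocol 8.7 names 4 (AUCtau, Cmax, Tmax, t1/2) plus Ctau if applicable. The SAP plans 0. Its table of contents goes from 8.2.1 straight to References.

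**3. Is the reduction declared?** SAP section 3 ties early termination with 9 enrolled subjects to listings only for efficacy, and promises both tables and listings for safety. PK is not mentioned. The two subsections on changes from the protocol are headed efficacy (6.3.3, blacked out) and safety (7.7). There is none for PK. The sentence in SAP section 1 about documenting changes in the CSR concerns changes made after the SAP is final, not a reduction inside it.

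**4. Internal consistency.** SAP 3.7 gives five display rules for concentration order statistics, triggered when values below the limit of quantitation occur in:
- at least 1 subject
- more than 25% of subjects
- more than 50%
- more than 75%
- all subjects

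It also sets an imputation of 0 at pre-dose and half the limit at later time points. The planned listing shows such values as BLQ and needs neither set of rules. Tables in section 8 to which the five rules would apply: 0.

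**5. Are the data available?** The Day 8 schedule has 8 time points. If all 9 enrolled subjects were dosed and fully sampled, that is 8 × 9 = 72 concentrations. The documents do not say that all were, so 72 is an upper limit.

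**The case against.** The strongest reply is that the SAP never withdraws protocol 8.7. It says it is based on the protocol, and it keeps the objective, the analysis sets and the summary conventions, so section 8 may simply be incomplete. That is fair as to intent, and no deliberate omission should be read into the text. It does not rescue the plan: SAP section 1 says the document sets out the methods and presentations for the CSR, and those contain no PK parameter.

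A second reply is that early termination, 9 subjects and a synoptic CSR explain abbreviated reporting. They are plausible reasons, but the SAP applies them explicitly only to efficacy, and it plans safety tables for the same subjects.

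Redaction does not explain the gap. The visible redactions are in 6.3 and none appears in section 8. Neither document cites a separate PK analysis plan.

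Some of the case against stands:
- The unused rules in 3.7 produce no wrong result.
- Protocol 8.7 itself fixes neither the time basis nor the Ctau sample, so on those details the SAP departs from nothing. They are gaps to close, and secondary to the main point.
- The listing carries actual dosing times, actual collection times and time since dose, so individual data are preserved.

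**Conclusion.** The concern holds and should be fixed. Section 8 of the SAP does not carry through protocol 8.7: 0 of the 5 protocol PK outputs and none of the named parameters are planned, the reduction is not declared, and the five display rules in SAP 3.7 have no table to serve.

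The consequence is limited. The endpoint is descriptive, no hypothesis or sample size depends on it, the rules for dose level and for opening Group B use DLT counts, and the listing keeps the underlying values.

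The conclusion assumes that no separate PK analysis plan exists, since neither document refers to one. If one does, the SAP should cite it.

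**What to change.** Add a subsection 8.2.2 to the SAP that:
- derives AUCtau, Cmax, Tmax, Ctau and, where estimable, t1/2 from the Cycle 1 Day 8 profile, on the PK Analysis Set, using actual sampling times
- states whether the pre-dose or the 12-hour sample defines Ctau
- provides the parameter listing, descriptive statistics, and linear and semi-log plots of protocol 8.7
- provides a concentration summary by time point, which the protocol synopsis calls for in general terms and SAP 3.7 presupposes.

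The cost is one extra listing, one or two summary tables and one set of plots, with no new samples or visits.

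If the sponsor prefers not to do this, add one paragraph to section 8 declaring and justifying the reduction as a change from the protocol-specified PK analyses, and remove or limit the concentration summary rules in 3.7 so that the two sections agree.

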## **10. SOFTWARE**

SAS® Software Version 9.4 or higher, SAS Institute Inc., Cary, NC, USA.

## 11. SAP REVISION

Revision Date (dd month, yyyy)	Section	Summary of Revision	Reason for Revision

**Appendix 1. Study Procedures Table: Group A (ENTO Monotherapy)**

Study Phase	Screening	Cycle 1				Subsequent Cycles		Remission/Relapse	End of Treatment (EOT)	30-day Follow-Up	Long Term Follow-up
Study Day	Screening	1	8	14	28	1	28				
Window (day)	-14	NA	±2	±2	±2	±2	±2	±2	±7	±7	± 4 weeks
General and Safety Assessments											
Informed Consent	X										
Medical & Medication History	X										
Adverse Events/Concomitant Medications	X	X	X	X	X	X	X		X	X	
Smoking status a	X	X				X					
Physical Exam	X	X		X		X			X		
Vital Signs b	X	X	X	X	X	X			X		
Height and Weight c	X	X				X			X		
ECG	X										
ECHO/MUGA	X										
Performance Status	X	X		X		X			X		
Chest X-ray	X										
Overall survival, treatments, and other malignancies											X (every 6 months)
Study Treatment											
ENTO Administration d		X	X	X	X	X	X				
Laboratory Assessments											
Chemistry e	X	X	X	X	X		X		X		
Hematology	X	X	X	X	X		X	X	X		
Coagulation	X			X	X		X		X		
Urinalysis	X										
Serum Pregnancy Test and FSH f	X										
Urine Pregnancy Test g		X				X			X		
HIV/HBV/HCV	X										
Sparse PK h		X		X	X		X				
Intensive PK i			X								
Disease Assessment j	X				X			X	X		

Study Phase	Screening	Cycle 1				Subsequent Cycles		Remission/Relapse	End of Treatment (EOT)	30-day Follow-Up	Long Term Follow-up
Study Day	Screening	1	8	14	28	1	28				
Window (day)	-14	NA	±2	±2	±2	±2	±2	±2	±7	±7	± 4 weeks
Bone Marrow Assessments											
Biopsy k	X				X			X	X		
Aspirate k	X				X			X	X		

- a Collect smoking status at screening and Day 1 of each cycle.
- b Vital signs include measurement of blood pressure, respiratory rate, pulse, temperature, and oxygen saturation level.
- c Height and weight will be measured at screening. Only weight will be measured on Day 1 of each cycle and at EOT.
- d ENTO will be administered BID on Days 1-28 for every 28 day-cycle as long as the subject is experiencing benefit and does not meet criteria for study treatment discontinuation. The subject may continue on ENTO monotherapy as long as the subject is experiencing benefit and does not meet criteria for study treatment discontinuation.
- e Include Total CPK at screening, Day 28 of every cycle, and EOT.
- f A negative serum pregnancy test is required for female subjects (unless surgically sterile or menopausal) at screening and a negative urine pregnancy test is required on Cycle 1 Day 1 prior to dose. Female subjects with medically documented ovarian failure must also have serum FSH levels within the institutional postmenopausal range at screening.
- g For females of childbearing potential, urine pregnancy tests will be done on Day 1 of each cycle and at EOT.
- h Peripheral blood samples for sparse PK will be obtained on Cycle 1 Days 1, 14 and 28, and Day 28 of subsequent cycles at pre-dose and 2hrs post-dose of ENTO.
- i Peripheral blood samples for intensive PK will be obtained on Cycle 1 Day 8 at 0 (pre-dose), 1, 2, 3, 4, 6, 8, and 12 hours post-dose of ENTO.
- j Subjects with hematologic malignancies other than AML will undergo the appropriate clinical, radiographic, laboratory procedures for disease assessment per the standard of care/institutional practice at screening (within 21 days before the first administration of study treatment), at the end of Cycle 1 on Day 28, as clinically indicated after Cycle 1, remission/relapse, and EOT (if not performed within the last 2 weeks).
- k Subjects with AML will undergo a bone marrow biopsy and aspirate (~8mL) for disease assessment at screening (within 21 days before the first administration of study treatment), at the end of Cycle 1 on Day 28, as clinically indicated after Cycle 1, remission/relapse, and EOT (if not collected within the last 2 weeks). Biopsy will be used in the event the aspirate cannot be collected or analyzed. Subjects with AML with cytogenetic and molecular mutations at screening must have cytogenetic and molecular mutation testing repeated at Cycle 1 Day 28, remission/relapse, and EOT.

